10.3 Risk Factor Management

Risk factor management at each site will be similar to that in the SAMMPRIS trial.⁵⁹ Each subject's risk factors will be managed by the study team. In addition, a health coach from the lifestyle modification program, INTERVENT (also used in SAMMPRIS) will be assigned to each subject. The study team will be required to follow the protocols established for the trial for the primary risk factors (LDL and blood pressure). The study team will also be responsible for the management of other risk factors (non-HDL cholesterol, diabetes targeting a hemoglobin A1c of < 7%, smoking, sedentary lifestyle, high body mass index) using national guidelines provided to each site. Assistance to the study team in achieving primary and secondary risk factor goals will be provided by the INTERVENT health coach and the subject's primary care physician (especially for management of diabetic medications). INTERVENT will call the subject by phone within the first week after randomization to complete enrollment in INTERVENT and schedule the first health coach call. Coaching calls will occur approximately every 2 weeks for the first 3 months, then once a month throughout follow-up. These calls typically last 15-20 minutes. At scheduled intervals, the INTERVENT health coach will generate a subject-specific Goals and Action Plan report that summarizes the recommendations for risk factor management, which is provided to the subject and the study site personnel. The INTERVENT counseling schedule will be staggered with the site study evaluation schedule in order to ensure that the most recent INTERVENT report is available to the study team for required follow-up evaluations.

Please refer to the Risk Factor Management Manual of Operations for more details of risk factor management.

10.3.1 Primary Risk Factors

Achieving Target LDL

The LDL management algorithm is described in detail in the Risk Factor Management Manual of Operations. In brief, baseline local laboratory values within 90 days prior or on the day of enrollment will qualify as the initial LDL levels for the determination of treatment. All subjects in

this trial with a baseline LDL \geq 1.8 mmol/L who are not already on a statin will be started on atorvastatin 40 mg per day. For subjects with a LDL \geq 1.8 mmol/L who are already on a statin, the dose will be increased to a dose equivalent to 40mg of atorvastatin (See **Table 2** for the equivalent doses of statins). For subjects on statins (e.g. pravastatin, lovastatin) whose maximum dose provides less LDL lowering effect than atorvastatin 40 mg per day, it is recommended that those subjects should be switched to atorvastatin 40 mg per day. For subjects with a baseline LDL \geq 1.8 mmol/L who are already on atorvastatin 40 mg, the dose will be increased to atorvastatin 80 mg.

All subjects with a baseline LDL \geq 1.8 mmol/L will have a repeat LDL measurement at the 30-day evaluation and if the 30-day LDL level is still \geq 1.8 mmol/L, their statin therapy will be increased (if not on a maximal dose) or ezetimibe or a PCSK9 inhibitor may be added (if already on a maximum tolerated dose of statin). A repeat LDL level should be measured 4-6 weeks after starting or changing the dose of any lipid-lowering medication. Additional titration of lipid lowering medications (including adding ezetimibe or a PCSK9 inhibitor if needed) should be continued until the subject's LDL is < 1.8 mmol/L. LDL levels will also be checked at the 1-year close-out evaluation in all subjects.

Table 2: Relative LDL-lowering Efficacy of Statin and Statin-based Therapies*								
Atorva	Fluva	Pitava	Lova	Prava	Rosuva	Vytorin**	Simva	% ↓ LDL-C
	40 mg	1 mg	20 mg	20 mg			10 mg	30%
10 mg	80 mg	2 mg	40 or 80 mg	40 mg			20 mg	38%
20 mg		4 mg	80 mg	80 mg	5 mg	10/10 mg	40 mg	41%
40 mg					10 mg	10/20 mg	80 mg	47%
80 mg					20 mg	10/40 mg		55%
					40 mg	10/80 mg		63%

Atorva = Atorvastatin; Fluva = Fluvastatin; Pitava = Pitavastatin; Lova = Lovastatin; Prava = Pravstatin; Rosuva = Rosuvastatin; Simva = Simvastatin

*Based on individual statin efficacy data, not head-to-head comparisons between statins.

**No incremental benefit of Vytorin on cardiovascular morbidity and mortality over and above that demonstrated for simvastatin has been established. http://www.fda.gov/Drugs/DrugSafety/ucm256581.htm

The study team will have access to lipid experts on the Risk Factor Management Committee about problems with individual subjects by contacting the Risk Factor Management Center.

Liver enzyme (AST and ALT) testing and creatine phosphokinase level (CPK) performed within 90 days prior to randomization (typically at the time of the qualifying stroke) will be considered the baseline values. Repeat testing will only be performed during the trial if clinically indicated. If repeat ALT or AST levels exceed 3x normal, the subject will return in 1 week for repeat testing. If the ALT or AST levels still exceed 3x normal, atorvastatin (or whatever statin the subject is on) will be stopped. Creatine phosphokinase level (CPK) should be repeated if the subject develops muscular symptoms during follow-up. If the CPK levels exceed 10x normal, depending on the associated clinical syndrome, the CPK level may be checked again within 1 week (e.g., if there is a history of recent trauma or strenuous exercise) or the atorvastatin (or whatever statin the subject is on) will be stopped (clinical evidence of myopathy).

Blood Pressure Management

The blood pressure management protocol is similar to that used in the SAMMPRIS trial.⁵⁹ See the Risk Factor Management Manual of Operations for the blood pressure management algorithm.

The study team at each clinical site will supervise hypertension management for CAPTIVA subjects. Study personnel are encouraged to use the CAPTIVA algorithm for managing blood pressure in the trial and adjust it, if necessary, based on individual subject characteristics, co-morbidities, and side-effects. The CAPTIVA Risk Factor Management Center will review blood pressure management at each clinical site on an ongoing basis. Study personnel will have access to blood pressure experts on the Risk Factor Management Center.

Blood pressure will be checked at each scheduled evaluation and subjects will be considered "in target" if the systolic blood pressure is <140 mmHg. For subjects above target, the blood pressure medications will be adjusted and a repeat BP check will be performed in approximately 30 days. Once the BP is in target, the subject resumes the next protocol scheduled evaluation (i.e., at 4, 8 or 12 months after randomization).

Selection of antihypertensives will be based on individual subject factors with emphasis on guideline-based regimens.

As part of routine care, all subjects will have serum creatinine, potassium, and sodium level checked prior to randomization, 30 days after starting or changing the dose of an ACE inhibitor, ARB, or diuretic and at 1 year to assess for alterations in renal function and electrolytes that could influence antihypertensive agent choice. Additionally, all subjects taking spironolactone (or other potassium-sparing diuretics) will have serum creatinine, potassium and sodium checked 7-14 days after starting or changing the dose as part of routine care.

10.3.2 Secondary Risk Factors

Non-HDL Cholesterol

Non-HDL cholesterol <2.6 mmol/L is considered an important secondary target. Non-HDL cholesterol consists of LDL plus the additional cholesterol carried by triglyceride rich lipoproteins - very low-density lipoproteins (VLDL) and intermediate density lipoproteins (IDL). Therefore, once LDL has been maximally treated, if non-HDL cholesterol \geq 2.6 mmol/L and fasting triglycerides are \geq 1.6 mmol/L mg/dl, refer to the Risk Factor Management Manual of Operations for management options or contact the Risk Factor Management Center.

Diabetes Management

Diabetes management will be performed by study personnel and the subject's outside physicians (primary care or diabetologist) to achieve a target HgA1c < 7.0% as per current standard of care. (unless there is a compelling reason for a less-stringent target, such as a subject with a history of severe hypoglycemia) based on the recommendations of the American Diabetes Association.⁷⁷

Smoking Cessation

Current smoking status will be assessed by the PACE Smoking Score at every evaluation. Smoking cessation will be strongly encouraged by the study team.

Targeted Weight Management

Weight will be assessed at each follow-up evaluation and BMI charts will be provided to each study team. The standard formula for calculating BMI is:

BMI = (Weight in Pounds / (Height in inches) x (Height in inches)) x 703

An online BMI Calculator can be found at:

http://www.nhlbi.nih.gov/guidelines/obesity/BMI/bmicalc.htm

The target goals for BMI in study subjects are as follows:

If the initial BMI is 25-27 kg/m², the target BMI is < 25 kg/m². If the initial BMI is > 27 kg/m², the target is a 10% weight loss.

Physical Activity

Physical activity status will be assessed by the PACE Current Physical Activity Status Score at every evaluation. Study personnel are encouraged to emphasize the importance of physical activity to the subject. Moderate intensity activities will be recommended at least 3 times per week (optimally five times per week) for 30 minutes per session in subjects able to participate.

Moderation of Alcohol

Subjects will be told to limit daily alcohol intake to 1 oz. of ethanol (2 oz. of 100-proof whiskey, 8 oz. of wine, 24 oz. of beer).

Schedule of Recommended Laboratory Tests to Monitor Risk Factors

The schedule of recommended standard of care tests to monitor risk factors and medications used for risk factor management are provided in **Appendix 2**.

11 SCHEDULE FOR FOLLOW-UP

All subjects in CAPTIVA will be evaluated at 1 month, 4 months, 8 months, and 1 year when they will have their blood pressure checked, risk factors optimized, and will be assessed for study endpoints. At these evaluations, pill counts of the study antithrombotic medications and aspirin tablets will be obtained. At each of these evaluations, subjects will also be asked about adverse events and changes in medications since the last evaluation. For subjects whose systolic blood pressure is greater than or equal to >140/90 mmHg at any evaluation, an adjustment in the blood pressure medications should be made and the subject's blood pressure level should be checked again 30 days later. The following definitions and windows will be used for follow-up evaluations:

Assessment	Window	Definition
Baseline		Randomization Day

1 month	±7 days	Day 23-37, inclusive
4 months	±7 days	Day 113-127, inclusive
8 months	±7 days	Day 233-247, inclusive
1 year	±7 days	Day 358-372, inclusive

12 EVALUATION OF ENDPOINTS AND ADVERSE EVENTS

The primary endpoint is ischemic stroke (using the AHA/ASA definition of stroke¹), ICH, or vascular death during 1 year of follow-up. Subjects will be carefully instructed to contact the study team immediately if they develop new neurological symptoms (or other adverse events), and site personnel must evaluate subjects as soon as possible after symptom onset. If the site personnel suspects that the symptoms are ischemic or hemorrhagic in nature, a brain MRI must be obtained as soon as possible and no later than 2 weeks after onset (head CT is permissible only if subject cannot tolerate or has contraindication to MRI). If MRI is not considered necessary as standard care, the study will pay for the MRI. All neuroimaging will be reviewed and adjudicated by the central neuroradiologist who is based at the University of Florida.

All reported neurological events and bleeding episodes will be adjudicated centrally by blinded stroke neurologists with extensive experience adjudicating such endpoints in other stroke trials. All myocardial infarctions and deaths will be adjudicated blinded to treatment assignment by cardiologist adjudicators who are experienced adjudicators in cardiology trials.

All subjects who are adjudicated as having a stroke during the study will continue on their assigned treatment that will remain blinded unless their treating physicians choose open-label antithrombotic therapy. These subjects will continue to be followed to one year after randomization.

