4.2 Efficacy Primary Endpoint

The primary efficacy endpoint is ischemic stroke, ICH, and vascular death.

The definition of ischemic stroke in CAPTIVA is the AHA definition that includes acute focal signs or symptoms of cerebral, spinal cord, or retinal involvement of any duration associated with imaging, pathological, or other objective evidence of arterial infarction OR clinical evidence of cerebral, spinal cord, or retinal focal arterial ischemic injury based on symptoms persisting ≥ 24 hours or until death, and other etiologies excluded.¹ ICH is defined by hemorrhage in parenchymal brain tissue detected by CT or MRI that is associated with new neurological symptoms (any of the following: headache, change in level of consciousness, focal neurological symptoms) or seizure. Vascular death is defined by sudden cardiac death without proven MI or death within 30 days of any of the following: ischemic stroke, ICH, non-ICH major hemorrhage, MI, congestive heart failure, cardiac or cerebral vascular procedure, pulmonary embolus, ruptured aortic aneurysm, or acute ischemia of a limb or internal organ.⁶¹

Secondary Efficacy Endpoints: Secondary endpoints are: 1) Composite of primary endpoint and MI (4th universal definition⁶²); 2) All stroke (ischemic and ICH); 3) Ischemic stroke; 4) ischemic stroke in the territory of the qualifying stenotic artery; 5) All death.

Exploratory Outcome Measure: Cognitive outcome at 12 months as measured by the Montreal Cognitive Assessment (MoCA) will be evaluated because there is significant interest in cognitive outcomes in subjects with stroke.^{63,64} The MoCA is a validated tool for detecting cognitive impairment.⁶⁵

Blinding. Subjects, investigators, study coordinators, and treating physicians will be blinded to allocation to the three arms. Subjects in all three arms will knowingly receive aspirin and intensive risk factor management through 1 year of follow-up.

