4.3 Unblinding

Unblinding (i.e., release of randomization assignment) will be performed if a compelling clinical reason arises. Requests for unblinding will typically originate from a treating physician because of an adverse event.

To preserve study integrity, every effort will be made to minimize unblinding of treatment assignments. Unblinding will only be allowed in the setting of a CAPTIVA subject's acute ischemic stroke, major hemorrhage, or other serious condition when planned acute treatment (other than stopping study antithrombotic medications) requires knowledge of the assigned antithrombotic treatment.

Refer to the Manual of Operation and Procedures (MOP) for detailed unblinding information.

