5.2 Exclusion Criteria

- 1. Previous treatment of target lesion with a stent, angioplasty, or other mechanical device, including mechanical thrombectomy for the qualifying stroke, or plan to perform one of these procedures
- 2. Plan to perform concomitant endarterectomy, angioplasty or stenting of an extracranial vessel tandem to the symptomatic intracranial stenosis
- 3. Intracranial tumor (except meningioma) or any intracranial vascular malformation
- 4. Thrombolytic therapy within 24 hours prior to randomization
- 5. Progressive neurological signs within 24 hours prior to randomization
- 6. History of any intracranial hemorrhage (parenchymal, subarachnoid, subdural, epidural)

asymptomatic radiographic microhemorrhages or hemorrhagic conversion of infarction are not exclusions but the latter requires delaying randomization for 2 weeks from onset of qualifying stroke

- 7. Intracranial arterial stenosis due to: arterial dissection; MoyaMoya disease; any known vasculitic disease; herpes zoster, varicella zoster or other viral vasculopathy; neurosyphilis; any other intracranial infection; any intracranial stenosis associated with CSF pleocytosis; radiation induced vasculopathy; fibromuscular dysplasia; sickle cell disease; neurofibromatosis; benign angiopathy of central nervous system; postpartum angiopathy; suspected vasospastic process; reversible cerebral vasoconstriction syndrome (RCVS); suspected recanalized embolus
- 8. Presence of any of the following unequivocal cardiac sources of embolism: chronic or paroxysmal atrial fibrillation, mitral stenosis, mechanical valve, endocarditis, intracardiac clot or vegetation, myocardial infarction within three months, left atrial spontaneous echo contrast
- 9. Known allergy or contraindication to aspirin, rivaroxaban, clopidogrel, or ticagrelor
- Uncontrolled severe hypertension (systolic pressure > 180 mm Hg or diastolic pressure > 115 mm Hg), active peptic ulcer disease, major systemic hemorrhage within 30 days prior to randomization, active bleed or bleeding diathesis, platelets < 100,000, hematocrit < 30, INR

> 1.5, clotting factor abnormality that increases the risk of bleeding, current alcohol or substance abuse, severe liver impairment (AST or ALT > 3 x normal, cirrhosis), or CrCl < 15 mL/min or on dialysis

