14 SAMPLE SIZE AND STATISTICAL ANALYSIS

Sample Size Determination for the Primary Safety Outcome

The safety analysis is prespecified to occur when the first 450 randomized subjects have completed the 1-year follow-up period, resulting in approximately 150 patient-years of follow-up in each arm. While the 450th subject is completing the 1-year follow-up period, enrollment projections (15 subjects per arm per month) suggest that an additional 180 subjects per arm will have been randomized. The follow-up time available for these additional subjects will vary but is expected to be approximately 6 months on average, for an additional 90 patient-years of follow-up (180*6/12) per arm. The safety analysis will use available data on all enrolled subjects and is therefore expected to include approximately 240 patient-years of follow-up per arm.

Within each treatment arm, an analysis will be conducted to evaluate an excess risk of ICH as well as non-ICH major hemorrhage. In SAMMPRIS, the ICH rate was 0.5 (exact 80% CI 0.05 - 1.9), and the non-ICH major hemorrhage rate was 2.4 (exact 80% CI 1.2 - 4.5), per 100 patient-years on clopidogrel + aspirin. Even though clopidogrel was only used for 90 days in SAMMPRIS

and will be used for 1 year in CAPTIVA, we are using the 80% CI of the SAMMPRIS rates to be conservative and not overestimate the hemorrhage rates on clopidogrel + aspirin. In each experimental arm, the hypothesis for the safety analysis is that the rate is greater than these upper 80% confidence limits derived from SAMMPRIS. This hypothesis will be tested with a one-sided 0.05 level of significance because we are only interested in identifying an increase in risk (not a decrease). If an experimental arm crosses this safety boundary, this will initiate an unplanned, for cause, futility analysis in order to weigh the risk:benefit ratio of the corresponding experimental arm. With 240 patient-years of follow-up, the safety analysis has 80% power to reject the stated null hypothesis for the true event rates shown in **Table 3**.

Table 3. Safety Analysis			
Safety Event	Null Hypothesis (per 100 patient-years)		
ICH	Rate ≤1.9		
Non-ICH major hemorrhage	Rate ≤4.5		

Sample Size Determination for the Primary Efficacy Outcome

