For the comparison of a single experimental arm to clopidogrel + aspirin, the sample size was calculated for a two-sample survival analysis using EAST v6. In order to detect a HR of 0.66 (decrease in events from 24% to 16.56%) with 80% power, using a two-sided 0.05 level of significance, the required sample size per comparison is 948 (474 per arm). This calculation includes inflation for an interim futility analysis, conducted according to an O'Brien-Fleming error spending function after 50% of events have occurred. The calculation also includes inflation to account for approximately 5% dropout, assuming that dropout is a competing risk. In SAMMPRIS, 3% in the medical arm were lost over the first year of follow-up, so our 5% drop out estimate at 12 months is reasonable. An additional inflation factor of ~1.18 is then applied to account for dilution of the treatment effect associated with approximately 8% non-compliance with antithrombotic therapy, yielding a sample size per comparison of 1122 subjects (561 per arm). The inflation factor is derived via $1/(1-R^2)$, where R represents the non-compliance rate, as suggested in Friedman, Furberg, and DeMets.⁷⁸ We expect the non-compliance will largely result from adverse events from the antithrombotic medications (major hemorrhages in all 3 arms and dyspnea in the ticagrelor arm) but we do not expect these rates will exceed 8% in 1 year of followup in any arm of the trial. We expect treatment crossover to be very low because it is unlikely that subjects who do not have a primary endpoint will be switched from their blinded treatment arm to

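### Section 12's default of continuing blinded treatment after a stroke is worded broadly enough to include ICH, and should be limited to ischemic stroke

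*Protocol*

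**What the plan says.** Section 12 of the protocol sets the rule for study drug after an on-study stroke. Once events have been adjudicated, all subjects "having a stroke during the study will continue on their assigned treatment that will remain blinded unless their treating physicians choose open-label antithrombotic therapy". They are then followed to one year after randomization. The rule applies to every such subject, uses the bare word stroke, and names one exception.

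Just before it, the same section describes who adjudicates: "All reported neurological events and bleeding episodes will be adjudicated centrally by blinded stroke neurologists". The opening line of Section 12 lists ischemic stroke and ICH as separate components of the primary endpoint.

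Elsewhere in the protocol:

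- Section 4.2 names as a secondary endpoint "All stroke (ischemic and ICH").
- Section 4.3 allows unblinding for an acute ischemic stroke and also for "major hemorrhage, or other serious condition when planned acute treatment (other than stopping study antithrombotic medications) requires knowledge of the assigned antithrombotic treatment".
- Section 14, in justifying the 8% non-compliance allowance, says: "We expect the non-compliance will largely result from adverse events from the antithrombotic medications (major hemorrhages in all 3 arms", with dyspnea in the ticagrelor arm also mentioned).
- Section 5.2, item 6, excludes at entry "History of any intracranial hemorrhage (parenchymal, subarachnoid, subdural, epidural"). It adds that asymptomatic microhemorrhages and "hemorrhagic conversion of infarction are not exclusions but the latter requires delaying randomization for 2 weeks from onset of qualifying stroke".

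**The concern.** ICH is both a primary safety endpoint and a component of the primary efficacy endpoint, so it is an event the trial expects to see. A site that looks up what to do with study drug afterwards finds one sentence on treatment after a stroke. It tells the site to carry on blinded unless the physician prefers an open-label antithrombotic. Stopping or holding drug because of a bleed is not named.

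If the word stroke includes ICH, the written default keeps a subject on aspirin plus ticagrelor, rivaroxaban or clopidogrel after a symptomatic brain hemorrhage. A site that stopped the drug, as sound care would normally require, would be departing from the text. What is at stake is patient safety and clear instructions to sites, not the statistical properties of the trial.

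**Working it through.** The question is mainly one of text, so the relevant places are set side by side. A short calculation then gives the scale.

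**1. Does the word stroke in Section 12 reach ICH?**

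- For: Section 4.2 puts ischemic stroke and ICH together under stroke. The adjudicators in Section 12 receive bleeding episodes as well as neurological events, so being adjudicated as having a stroke is not confined to ischemic events by the process. Where Section 12 means ischemic stroke alone, in its opening line, it says ischemic.
- Against: that same opening line attaches the AHA/ASA definition of stroke to the ischemic component and lists ICH apart from it. An open-label antithrombotic switch is a natural response to ischemic recurrence, not to a bleed.
- Result: the literal wording includes ICH; the probable intent does not.

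**2. Does other text agree with the literal wording?**

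- Section 4.3 treats stopping study antithrombotics as an available response to major hemorrhage that does not need unblinding. The protocol's recurring term non-ICH major hemorrhage implies that ICH is itself a major hemorrhage.
- Section 14 expects major hemorrhage in every arm to be a source of non-compliance with study drug.
- Result: both presuppose stopping, so the literal Section 12 default conflicts with them. Neither is an instruction to sites.

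**3. Does anything override the sentence?** The only explicit instruction in the protocol to discontinue study drug for a clinical event is for pregnancy (Section 5.2, item 15). There is no corresponding rule for ICH.

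**4. How often would the situation arise?**

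Inputs, both from Section 14:

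- 561 subjects per arm. With full one-year follow-up assumed, this gives 561 patient-years per arm.
- "In SAMMPRIS, the ICH rate was 0.5 (exact 80% CI 0.05 - 1.9") per 100 patient-years on clopidogrel + aspirin.

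Expected ICH per arm = patient-years × rate / 100:

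| Rate per 100 patient-years | Calculation | ICH per arm |
|---|---|---|
| 0.5 (point estimate) | 561 × 0.005 | 2.8 |
| 0.05 (lower 80% limit) | 561 × 0.0005 | 0.3 |
| 1.9 (upper 80% limit) | 561 × 0.019 | 10.7 |

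Section 14 notes that clopidogrel was used for only 90 days in SAMMPRIS, and it anticipates more bleeding in the two experimental arms, so the true counts could be higher. The table counts ICH events, not subjects kept on drug because of the sentence. The protocol gives no basis for estimating the latter.

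**5. Is there a statistical consequence?** ICH is itself a primary endpoint event and the primary comparison is of time to event, so whether drug is continued after an ICH does not change when that subject reached the primary endpoint. At the point estimate, holding drug after ICH affects 2.8 / 561 = 0.5% of an arm, set against an 8% non-compliance allowance that already cites major hemorrhage.

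**The case against.** The strongest reply is that too much is being drawn from one missing adjective. The endpoint definitions keep ICH separate from ischemic stroke, and the Section 4.2 phrase needs the word all and a parenthesis to bring ICH in. The open-label exception makes sense only for ischemic recurrence. Sections 4.3 and 14 show that stopping after hemorrhage is contemplated. The sentence also takes effect only once a stroke has been adjudicated centrally, after reporting and imaging that may come up to two weeks after onset, so bedside decisions about a bleed will already have been made. The manual of procedures may give site instructions, though its content is not known here.

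Most of this stands, and it sets the severity. It shows that nobody is likely to have intended treatment through ICH, and that few physicians would act that way. It does not make the sentence correct: an operative rule addressed to all subjects should not depend on readers supplying a missing word, and the texts pointing the other way mention stopping only in passing.

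Two stronger readings are tempting. A reader might infer that the protocol requires, or was designed to require, study drug to continue after ICH. The documents do not support that: nothing forbids stopping, and Sections 4.3 and 14 assume it can happen. A reader might also see a contradiction with the entry criteria. Those govern entry only, and hemorrhagic conversion is expressly not an exclusion. The bar on prior intracranial hemorrhage is, if anything, further evidence that ICH was never meant to fall under the Section 12 default.

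**Conclusion.** The point holds as a low-severity safety wording error. The Section 12 default is broader than it should be: taken with Section 4.2 it includes ICH, its only exception does not fit a bleed, and it conflicts with what Sections 4.3 and 14 presuppose. Ischemic stroke was almost certainly intended.

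The setting is uncommon but likely to occur: about 3 ICH per arm (0.3 to 10.7), assuming the SAMMPRIS rate carries over and follow-up is complete. It would be wrong to infer that about 3 subjects per arm would be kept on drug; that number is unknown and probably very small. There is no effect on power, bias or sample size.

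**What to change.** In the Section 12 sentence, change a stroke to *an ischemic stroke*. Then add: *After an ICH, study antithrombotic medication and aspirin are held; any restart is at the treating physician's decision. Follow-up continues to one year after randomization.*

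The one-word change removes the over-broad default. The addition gives sites a positive instruction where the protocol now has none, and keeps these subjects in follow-up.

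The cost is one amended sentence with its addition, and a site memo. No extra subjects, visits or procedures are needed.
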